#### **Secondary Efficacy Endpoint**

- Clinical Global Impression of Change (CGI-C) – this clinician-administered interview is important for demonstrating that improvements in cognition correspond to an overall functional improvement - an FDA requirement for approval of a cognition-enhancing drug for schizophrenia patients.

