#### **Tertiary/Exploratory Efficacy Endpoints**

- MCCB composite score – a common efficacy endpoint in trials of drugs for cognition enhancement in schizophrenia and schizoaffective disorder, providing evidence of global cognitive improvement.
- MCCB individual subscales and supplementary cognitive tests – these subscales and tests will provide additional information regarding the efficacy of MMFS for improving specific cognitive domains in patients with schizophrenia or schizoaffective disorder. We believe that MMFS may improve other aspects of cognition in addition to working memory, especially those that involve frontal cortex function.
- A working memory composite score derived from the two MCCB working memory subscale tests along with the Brown-Peterson's Auditory Consonant Trigrams test. Deriving a composite score from 3 working memory tests may be superior to the MCCB working memory subscale, which is a composite comprised of only 2 working memory tests. This possibility will be tested to identify the best composite measure of working memory for future trials.
- Responder analysis – the number of subjects achieving a clinical significance cutoff of improving at least one half of a standard deviation (T-score change  $\geq 5$ ) on the working memory subscale of the MCCB, to evaluate the clinical significance of any MMFS treatment effects; an analogous approach will be employed for secondary outcomes.
- Positive and negative symptoms – Positive symptoms will be assessed with the PANSS positive

scale, and negative symptoms will be assessed with the PANSS negative scale and the BNSS. We hypothesize that MMFS-202-302 may significantly improve negative and positive symptoms, at least partially independently from its cognition enhancing effects.

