## 8.0 STATISTICAL CONSIDERATIONS

### 8.1 Analysis of Clinical Data

Data will first be analyzed for efficacy on a per-protocol basis. The per-protocol population will include all subjects who complete all scheduled visits (+/- 5 days from planned visit time), have no protocol deviations that in the judgment of the principal investigator would invalidate their efficacy data, and achieve medication compliance of 80-120% (determined by pill counting; if pill packs are not available for confirmation, self-report of compliance will be used). Participants whose assessment falls +10 days or less from the scheduled visit will be included in per-protocol population, only if they were taking the study compound throughout. Data will secondarily be analyzed for efficacy on an intent-to-treat basis, with last observation carried forward (LOCF) for missing values or dropouts; subjects who did not receive any study compound will be excluded from the full analysis set, preserving the intent-to-treat principle. The primary analysis will be a univariate ANCOVA adjusting for baseline differences in the dependent measures of interest. We would also examine some variables categorically. The MATRICS working memory subscale T-score at 9 weeks will be the primary endpoint. Secondary endpoints will include the Clinical Global Impression of Change (CGI-C); the MCCB composite score; other individual cognitive domain subscale T-scores of the MCCB; a working memory composite score comprised of the 2 MCCB working memory subscale tests and the ACT test; and the PANSS positive and negative scales and BNSS. All endpoints will be evaluated as 9-weeks change from baseline, except for PANSS, which will be evaluated at both 6 and 9 weeks compared to baseline. Responder analyses will also be carried out using a chi-square test for the MCCB working memory subscale as a secondary endpoint evaluating clinical significance, using a cutoff of 0.5 standard deviation improvement (T-score improvement of  $\geq$  5 points). Finally, separate exploratory subgroup analyses will be performed on the MCCB working memory subscale T-score restricted to the subset of subjects who score 0, 0.5, or 1.0 SD or below the mean for normal age-matched normative data for that subscale. Analogous subgroup analyses will also be performed for the MCCB composite score, and the other MCCB subscale scores.

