Alpha will be set at 0.05 for all analyses. The individual scores for each of the 6 other neuropsychological MCB subscales, and supplementary cognitive tests (ACT, WCST, FAS), as well as the CGI-C measure of functional change will be evaluated to provide supporting information for primary and secondary measures.

Assumptions for the power analysis included random assignment into one group receiving placebo and one MMFS-202-302. The MCB, as the primary instrument will be collected at baseline and at end point (9 weeks). Using univariate ANCOVA with baseline score as covariate, the time average difference in the response variable will be compared between groups to detect treatment difference. Based on Javitt et al, 2012, we assume the mean baseline working memory score will be 36.4, SD 11.7 for both groups. We assume the placebo group will show no improvement with an SD of change of 6.5, while the treatment group will improve a mean of 5 points with the same SD of change, a medium effect. We assume the correlation coefficient of repeated observation to be 0.5 and the covariance structure to be compound symmetry. The power calculation was conducted with alpha level of 0.05. Full results are available upon request. With a two-sided test, the analysis reveals that 28 subjects per group are required assuming 5 points of improvement of the treatment group compared to the placebo for the desired power of 80% with alpha level of 0.05. We plan to recruit 30 per group to account for drop outs. Thus, allowing for attrition up to 20%, this sample size will provide 74-83% power to detect the hypothesized medium treatment effect.

We will assess MMFS-202-302 effects on negative and positive symptoms as additional endpoints, as measured by the BNSS and PANSS. Further, we will analyze the effect on drug tolerability as determined by the following: body weight, body mass index (BMI), waist circumference, and movement rating scales.

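### The working-memory responder analysis is a valid but unadjusted chi-square; adjusting it for baseline, as the primary ANCOVA does, is a cheap, low-priority gain in precision

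*Combined protocol and SAP*

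**What the plan says.** Section 8.1 (Analysis of Clinical Data) says of the main analysis: "The primary analysis will be a univariate ANCOVA adjusting for baseline differences in the dependent measures of interest". The power paragraph repeats the covariate: "Using univariate ANCOVA with baseline score as covariate".

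For responders on the same working-memory score, section 8.1 says: "Responder analyses will also be carried out using a chi-square test for the MCCB working memory subscale". It describes this analysis "as a secondary endpoint evaluating clinical significance, using a cutoff of 0.5 standard deviation improvement", which it equates to a T-score gain of at least 5. No covariate, stratification, effect measure or confidence interval is named.

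Section 3.0 lists the responder analysis among the tertiary and exploratory endpoints, with the aim "to evaluate the clinical significance of any MMFS treatment effects", and extends the approach to the secondary outcomes. Its rank therefore differs between the two sections. Section 3.0 also gives CGI-C a role on clinical relevance, as "important for demonstrating that improvements in cognition correspond to an overall functional improvement".

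The significance level is common to every test: "Alpha will be set at 0.05 for all analyses". Section 7.0 describes permuted blocks that limit imbalance in group sizes. It mentions no stratification by baseline score.

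**The concern.** Whether a patient gains 5 points depends partly on where that patient starts. Low baseline scores tend to move up on retest and high ones down. Defining response by change subtracts the baseline but does not remove this regression to the mean.

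The primary ANCOVA adjusts for it and the responder test does not. With about 30 patients per arm and no stratification on the score, some chance difference in baseline is to be expected. It adds avoidable noise to the responder comparison and can pull that comparison away from the ANCOVA. At stake is the precision of one supportive analysis, not the primary inference.

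**Working it through.** **Inputs (section 8.1 unless noted).** Baseline mean 36.4, SD 11.7. For placebo: "We assume the placebo group will show no improvement with an SD of change of 6.5". Treated mean change 5 with the same SD. Correlation 0.5 under compound symmetry. Two-sided alpha 0.05. Sixty patients randomized 1:1 (section 2.0), hence 30 per arm, or 24 after 20% attrition. Response cutoff 5.

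**1. The plan's own figure.** A two-sample t-test on change with difference 5 and SD 6.5 (noncentral t) has power 74.2%, 80.7% and 83.4% at 24, 28 and 30 per arm. This reproduces the stated 28 per group and the 74-83% range. No gain from the baseline covariate is built in.

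**2. The variance inputs conflict.** Under compound symmetry, SD of change = SD × √(2(1 − r)).
- SD 11.7 with r = 0.5 gives 11.7, not 6.5.
- SD 11.7 with SD of change 6.5 gives r = 1 − 6.5²/(2 × 11.7²) = 0.846.

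Three settings are therefore carried, each keeping two of the three inputs:
- A: SD 11.7, SD of change 6.5 (r = 0.846)
- B: SD 11.7, r = 0.5 (SD of change 11.7)
- C: SD of change 6.5, r = 0.5 (SD 6.5)

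**3. Responder rates and chi-square power.** With normal changes, the placebo rate is P(Z ≥ 5/SD of change) and the treated rate is 50%.
- SD of change 6.5: P(Z ≥ 0.769) = 22.1% against 50%. Power is 52%, 59% and 62% at 24, 28 and 30 per arm; 80% power needs 46 per arm. Against step 1, the loss from dichotomizing is 74 − 52 = 22, 81 − 59 = 22 and 83 − 62 = 21 points.
- SD of change 11.7: P(Z ≥ 0.427) = 33.5% against 50%. Power is 21%, 24% and 25%.

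**4. Dependence of change on baseline.** Corr(change, baseline) = −√((1 − r)/2). This is −0.28 in A and −0.50 in B and C.

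**5. Effect of a chance imbalance.** The standard error of the baseline difference at 30 per arm is SD × √(2/30): 3.02 points in A and B, 1.68 in C. Per point of imbalance, the responder difference moves by −(1 − r) × f, where f is the density of change at the cutoff, averaged over the arms.

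| Setting | 1 − r | f, placebo | f, treated (+5) | Shift per 1 SE, no effect | Shift per 1 SE, 5-point effect |
|---|---|---|---|---|---|
| A | 0.154 | 0.0457 | 0.0614 | −2.1 pp | −2.5 pp |
| B | 0.5 | 0.0311 | 0.0341 | −4.7 pp | −4.9 pp |
| C | 0.5 | 0.0457 | 0.0614 | −3.8 pp | −4.5 pp |

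Worked for A with a 5-point effect: −0.154 × (0.0457 + 0.0614)/2 × 3.02 = −0.025. Simulated slopes agree (−2.6, −4.9 and −4.5 pp).

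**6. Chi-square against the baseline-adjusted logistic score test.** There were 20,000 simulated trials per setting, so the Monte Carlo SE is about 0.15 points for type I error and 0.35 for power. The adjusted test's power is taken at its own simulated 5% critical value; the chi-square is left at its nominal one.

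| Setting, n per arm | Type I: chi-square / score / likelihood ratio | Power: chi-square | Power: score, size-corrected | Gain |
|---|---|---|---|---|
| A, 28 | 4.8 / 5.5 / 6.0% | 60.4% | 60.4% | 0.0 |
| A, 30 | 4.6 / 5.1 / 5.7% | 62.0% | 64.6% | 2.6 |
| B, 28 | 4.9 / 5.0 / 5.4% | 23.2% | 28.3% | 5.1 |
| B, 30 | 4.7 / 5.4 / 5.6% | 25.3% | 28.8% | 3.5 |
| C, 28 | 4.8 / 5.6 / 6.2% | 60.1% | 65.0% | 4.9 |
| C, 30 | 4.8 / 5.5 / 6.0% | 62.2% | 69.0% | 6.8 |

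Across separate runs, the chi-square's type I error was 4.6% to 5.2%. In trials with a baseline imbalance above 1 SE it was about 5% in A and 7-8% in B and C. After adjustment, the dependence of the responder difference on baseline imbalance was about zero and its standard error fell by about 1-8%.

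**The case against.** The strongest reply is that nothing here is an error. A chi-square on a randomized two-by-two table is valid, and chance imbalance is already part of its 5%. Response is defined by change, so baseline already enters. Inference on this score rests on the ANCOVA, which does adjust. Part of any apparent power gain from a likelihood-ratio test comes from that test running above 5%. Most disagreement between the ANCOVA and the responder test comes from dichotomizing, which a logistic model keeps.

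All of this stands, and it rules out several stronger readings that a reader might draw:
- That the chi-square is biased or inflates type I error. Overall it does not. The 7-8% figure is conditional on a large imbalance and applies only with r = 0.5.
- That baseline is ignored. Only the remaining dependence of change on baseline is unadjusted.
- That omitting baseline is the main loss of power. Dichotomizing costs far more.
- That this is the plan's only evidence on clinical significance. CGI-C also bears on it.
- That clinical significance will be read from a raw count of responders. A placebo rate of 22% to 33% would make such a count uninformative, but the plan compares arms.

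What survives is that the covariate is already collected and already used for the same score, and that leaving it out costs some precision at no saving.

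**Conclusion.** The point holds as a low-priority improvement. The responder test is valid but less precise than it could be. A one-SE baseline imbalance at 30 per arm moves the responder difference by about 2 to 5 percentage points. Adjustment removes that movement and adds about 0 to 7 points of size-corrected power at 28 to 30 per arm: about 0 to 3 with SD 11.7 and SD of change 6.5, and about 3 to 7 with r = 0.5. The case rests more on consistency with the ANCOVA than on power.

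The figures assume normal scores, equal SDs at both visits, a constant 5-point effect and a randomized comparison. Section 8.1 analyses a per-protocol set first, and randomization does not by itself guarantee balance there. The range reflects the conflict among the plan's variance inputs and cannot be narrowed from the documents. The 21 to 22 points lost to dichotomizing apply to an SD of change of 6.5, and adjustment does not restore them.

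**What to change.** In section 8.1, make the responder analysis a logistic regression of response on arm and continuous baseline T-score. Name the score test in advance. Report the baseline-standardized risk difference with its 95% CI, and keep the chi-square as a sensitivity analysis. Use the same model, each with its own baseline score, for the analogous responder analyses in section 3.0. In the same edit, give the responder analysis one rank in sections 3.0 and 8.1.

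The cost is a few lines of SAP wording and code, with no new data. The downside is a slightly more complex analysis than a two-by-two table. The choice of test matters: a likelihood-ratio test runs at about 5.5-6.5% at these sample sizes, whereas the score test ran at about 5.0-5.9%, closer to the chi-square.

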### **8.2 Analysis of Structural Imaging Data**

Structural MRI will be processed with the FreeSurfer (FS) image analysis suite (<http://surfer.nmr.mgh.harvard.edu/>) [20], followed by FS+LDDMM [21] for the high-dimensional mappings of the subcortical and cortical ROIs. These automated methods produce anatomic measures that are equivalent to measures made by experts, but with increased reproducibility and decreased manual effort [22]. Maps of longitudinal change are then computed by applying within-subject FS+LDDMM where the subject's baseline scan becomes a template and each of the follow-up scans becomes the target, which carry the baseline ROIs into follow-up scans. Subcortical ROI volumes at each time point are calculated as volumes occupied by the mapped subcortical ROI. Subcortical ROI shape at each time point will be computed using principal components analysis (PCA) represented by the associated subject scores [22]. Cortical thickness, volume and metric distortion (representing local volume and folding change) at each time point are provided by FS [23].

### **8.3 Analysis of Functional Imaging Data**

Mixed effects models and analysis of variance will be used to evaluate behavioral performance on tasks administered in the scanner to characterize working memory performance and reward valuation across task conditions and to contrast performance between MMFS-202-302 vs. placebo treated groups. Event-related fMRI analyses will be carried out using SPM v8.0 (Statistical Parametric Mapping version 8.0 <http://www.fil.ion.ucl.ac.uk/spm/software/spm8/>) in a MATLAB environment. A fixed effect analysis will be used to model activation associated during events of interest in each subjects' time series data. Activation maps from these analyses will be carried forward to higher-level mixed effects analyses to model each group's activation during the events of interest allowing for separate estimations of variances for each group. Analyses contrasting activation in the MMFS-202-302 vs. placebo groups will include both whole brain and a priori regions of interest (i.e., DLPFC, PPC, OMPFC, ACC, NAc).

### **8.4 Analysis of EEG data**

EEG data will be analyzed using custom scripts designed by the laboratory of the PI and Co-I using MATLAB software ([www.mathworks.com](http://www.mathworks.com)). Statistical analysis methods will be used that are standard for behavioral data in learning and memory experiments for EEG data. These include individual as well as group-level statistics that permit inferences regarding the population (e.g., ANOVA, MANCOVA, Causal Modeling, ICA, etc.). To address the hypotheses, we will identify EEG patterns of variation across experimental tasks and determine how these patterns change across the age groups listed above.

Analysis of clinical, imaging, and EEG data will be completed by [name], [name], and

[name], MS, all of whom are experts in biostatistics and analytics.

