## 2.0 OVERVIEW OF STUDY DESIGN

### Patient population

All patients will meet criteria for DSM-V diagnosis of schizophrenia or schizoaffective disorder. At the time of enrollment, they will have been receiving a stable dose of an atypical antipsychotic drug for 2 months or longer and have stable positive symptoms, i.e. delusions or auditory hallucinations, at the screening visit. 60 patients will be enrolled, and randomized in a 1:1 ratio to one dose of MMFS-202-302 or placebo.

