### 2.1 STUDY OBJECTIVES

1. To determine the effectiveness of 9 weeks' supplementation with MMFS-202-302 as augmentation of atypical antipsychotic medication, to improve working memory or other specific domains of cognitive function, e.g. attention, executive function, declarative memory, etc., in patients with schizophrenia or schizoaffective disorder. The primary outcome measure will be a main effect of group on the 9-wk-change-from-baseline working memory subscale of the MATRICS Cognitive Consensus Battery (MCCB). The MCCB consists of 10 cognitive tests covering seven domains. This will be augmented by additional neuropsychological measures of verbal fluency (FAS Phonemic Fluency), working memory (Brown-Peterson's Auditory Consonant Trigrams) and executive function (the Wisconsin Card Sorting Test). The MCCB composite score, and each of the additional cognitive domain subscales listed above will be secondary outcome measures.
2. To determine the effect of MMFS-202-302 on global function, as measured by the Clinical

Global Impressions Scale (CGI) assessment of change (CGI-C).

3. To determine the effect of MMFS-202-302 on negative symptoms of schizophrenia, as measured by the Brief Negative Symptom Scale (BNSS) and PANSS negative subscale, and imaging of brain reward networks (OMPFC, ACC, NAc, VTA).
4. To determine the effect of MMFS-202-302 on positive symptoms of schizophrenia, as measured by the PANSS positive subscale.
5. To determine the effect of MMFS-202-302 as augmentation of atypical antipsychotic medication on both the behavioral performance and activation patterns in schizophrenia patients during a WM neuroimaging paradigm. Specifically, investigation in whether improvement from baseline task performance occurs for the MMFS-202-302 + APD group, and if this improvement is associated with increases in WM-related brain region activation (DLPFC & PPC).
6. To evaluate whether MMFS-202-302 results in greater functional connectivity within identified reward and working memory circuits in subjects with schizophrenia.
7. To determine whether MMFS-202-302 stimulates an overall enhancement or restoration of typical structural brain abnormalities in schizophrenia, as measured by cortical volume and thickness of the neocortex.
8. To examine the effect of MMFS-202-302 on neural connectivity and activation in EEG assessment, using measurements of learning and memory.

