### **4.1 Inclusion Criteria**

1. All patients must be capable of giving written informed consent.
2. Male or female subjects of any race; between 18 to 60 years of age, inclusive.
3. No hospitalization other than for evaluation in the past four months
4. Resides in a stable living situation, according to the investigator's judgment.
5. Diagnosis of schizophrenia or schizoaffective disorder of at least one year duration, as established by the SCID-I, and verified with medical records and/or confirmation of diagnosis by treating clinician. The illness is in a nonacute phase as determined by the subject's primary treating clinician
6. Current psychotropic drug treatment consists of monotherapy with an atypical antipsychotic drug.
7. No more than a mild level of EPS as determined by the Simpson Angus Scale (SAS) total score:  $\leq 6$
8. Not taking anticholinergic medication for EPS
9. No evidence of tardive dyskinesia
10. Subjects healthy enough to complete a 9-week clinical trial
11. Women of childbearing potential must have a negative pregnancy test at screening and baseline, and agree to use adequate protection (i.e. double barrier method) for birth control.
12. Able to complete cognition assessments in English
13. General intellectual abilities falling broadly within the average estimated IQ  $\geq 80$ , as measured by the *Wide Range Achievement Test – 4th Edition (WRAT-IV)*.

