## 7.0 RANDOMIZATION METHOD

Those who meet the study inclusion criteria will be randomized into one of two treatment groups, one to receive adjunctive therapy of MMFS-202-302 and the other to receive placebo. Using SAS software, a computer-generated randomization sequences for each treatment arm will be assigned using permuted block method limiting imbalance in numbers between groups. To assign the randomization, the SAS procedure PROC PLAN will be used [19]. Until the trial is concluded, the randomization sequence will be blind to the study participants as well as research coordinators and raters. Randomization list will be provided by assigned statistician, [name], and will be held by unblinded study drug manager at [name].

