#### **9.1.15 EEG Assessments**

Research participants will undergo EEG recording while participating in learning and memory tests at baseline and end of study visits. Prior to the experiment, research participants will be familiarized with EEG and prepared for the EEG recording session. Research staff will inform the research participants about the EEG procedures, and will ask the research participants to perform familiarization activities such as wearing the elastic caps that will be worn during the actual experiment (but without EEG recording) and showing the research participants informational videos and images of other individuals engaged in EEG recording.

After this familiarization process has finished, research participants will be prepared for EEG recording. This involves placing an elastic cap on the head of the research participant. Recording electrodes are embedded within the elastic cap, and these electrodes record the electrical activity of the research participants' brains non-invasively. The EEG apparatus is battery-powered, and poses no serious risk of physical harm to the research participant. Each recording electrode is filled with a non-toxic, hypoallergenic electrolytic gel so that the electrode makes contact with the participant's skin. The gel is injected using a blunt, plastic-tip syringe that poses minimal risk of skin abrasion because it is blunt and made of plastic. Electrodes are also affixed to the cheeks, temple area, and behind the ears using medical-grade tape that can be easily removed after the experiment. Participants then take part in the learning/memory testing during EEG recording. When the experiment is finished, the elastic cap is removed and participants are given the option to either wash the gel out of their hair in a sink provided in

the same laboratory (with help from the research staff as needed), or to simply leave and wash the gel out at home. Participants are then debriefed and dismissed. There are no known lasting physical ramifications of the EEG procedure. The only known risk to the research participant is the mild discomfort associated with wearing the EEG cap and possible frustration with the learning and memory tasks.

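### Section 8.4 compares EEG patterns across age groups that the trial does not have, so the EEG analysis as written does not test the drug effect in Objective 8

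*Combined protocol and SAP*

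**What the plan says.** Section 2.1, item 8, sets the EEG objective: "To examine the effect of MMFS-202-302 on neural connectivity and activation in EEG assessment, using measurements of learning and memory". Section 9.1.15 gives the timing: "Research participants will undergo EEG recording while participating in learning and memory tests at baseline and end of study visits". Appendix 1 agrees, marking EEG at day 1 and at the final visit.

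Section 8.4 is the only analysis text for these data. It promises "individual as well as group-level statistics that permit inferences regarding the population" and illustrates this with an open-ended list of methods, from analysis of variance to causal modelling and independent component analysis. One sentence then says how the hypotheses will be addressed: identify how EEG patterns vary over the tasks, and "determine how these patterns change across the age groups listed above".

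The design has no such groups. Section 2.0 states that "60 patients will be enrolled, and randomized in a 1:1 ratio to one dose of MMFS-202-302 or placebo". Section 7.0 has patients "randomized into one of two treatment groups". Section 4.1 sets a single eligibility range, "between 18 to 60 years of age, inclusive", with no strata inside it.

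**The concern.** The objective is about a drug effect, and in a randomised trial that calls for a comparison between arms. The one sentence that links the EEG data to the hypotheses names a different grouping factor, and that factor does not exist here. Anyone following Section 8.4 literally would reach a step that cannot be carried out, and no other sentence in the section supplies the missing contrast.

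What is at stake is the weight of any EEG finding. EEG offers many possible measures, the method list is open, and Section 8.1 sets alpha at 0.05 for all analyses. If the contrast, the measures and the model are settled only once results can be seen, a nominally significant EEG result would be hard to distinguish from selection. Participants are asked for two EEG sessions to serve this objective.

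**Working it through.** The plan gives no EEG effect size, standard deviation, correlation or power, so there is no figure to reproduce. The check is a reading of every mention of EEG, age and group.

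1. **Is there an age grouping anywhere?** Age appears in three ways: as the 18 to 60 eligibility range (Section 4.1); as age-matched norms for the MCCB cutoffs (Sections 3.0 and 8.1); and in the account of a previous trial in older adults (Section 1.1.2). None divides this trial's patients by age. Age groups defined: 0.

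2. **What groups exist?** Sections 2.0, 5.1 and 7.0 all describe MMFS-202-302 and placebo. Treatment groups defined: 2.

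3. **Does Section 8.4 name a treatment contrast or a change from baseline?** No. It mentions neither the drug nor placebo, and neither visit. EEG contrasts between arms specified: 0.

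4. **Does another section fill the gap?** Section 1.1.3 says EEG will be examined for differences over the course of the trial and refers the reader to Sections 5.0, 7.4 and 8.1. There is no Section 7.4, and Sections 5.0 and 8.1 do not mention EEG. Section 3.0 lists no EEG endpoint.

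5. **How do the neighbouring sections handle this?** Section 8.3 states the MMFS-202-302 versus placebo comparison for fMRI, both for task performance and for activation. Section 8.1 specifies ANCOVA adjusted for baseline for the clinical measures. Both elements needed for EEG are therefore already in the document, but are not applied to EEG.

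6. **Are the necessary data collected?** Yes. EEG is scheduled at baseline and at end of study, day 63 (9 weeks × 7 days = 63), with the same schedule for both arms.

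Taken together: the objective is stated and suitable data are collected, but the written analysis does not connect the two.

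**The case against.** The strongest reply is that this is a dangling phrase and that the intention is clear. The sentence opens by referring to the hypotheses; the only stated EEG objective is the effect of MMFS-202-302; group-level statistics do not exclude treatment; and treatment is the only grouping in the trial. Since the age comparison cannot be run, nobody would obtain a wrong EEG answer from it. This stands as an account of what was probably meant. It does not make the plan specify it, because the sentence names its own factor and that factor is not treatment.

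A second reply is that the omission is not peculiar to EEG: Section 8.2 names no arm contrast for structural MRI either. That is true, but Section 8.2 is silent on the contrast, whereas Section 8.4 states one that does not fit the design.

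A third reply concerns weight: EEG is exploratory in all but name. That stands, and it limits the point to a secondary correction.

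Two stronger readings are tempting, and the documents support neither. A reader might infer that the EEG data cannot answer Objective 8. They can, because randomised arms with recordings at both visits allow a valid comparison; only the written contrast fails. A reader might also want to express the loss as a percentage of precision forgone by not adjusting for baseline. The documents give no EEG correlation to support such a figure, and the plan nowhere proposes a comparison of end-of-study values alone against which to measure it.

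**Conclusion.** The point holds as a defect in the written EEG analysis. Section 8.4 specifies a comparison across groups that the trial does not define and specifies none between the groups it does define, so Objective 8 has no prespecified test. The size is qualitative: one objective of eight, the last listed and outside the Section 3.0 endpoints. The primary analysis, sample size and power are untouched.

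The conclusion rests on the available text. The schema figure is not shown, but every design statement that can be read describes two arms and no age strata. A reader might infer that the phrase was carried over from another protocol. The documents do not show that, and the conclusion does not depend on it.

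**What to change.** In Section 8.4, delete the age-group reference and replace it with a statement such as: *For each EEG measure named before unblinding, the week-9 value will be compared between MMFS-202-302 and placebo by ANCOVA with the baseline value of that measure as covariate. Results are exploratory.*

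Three details make this effective:

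- The measures, and the tasks they come from, should be listed. A correct contrast applied to an unlimited set of measures would leave selection almost as free as now.
- Only one model should be given for the treatment comparison, to match Section 8.1. The open method list should be confined to deriving the measures.
- The cross-reference in Section 1.1.3 should point to Section 8.4 in place of the non-existent Section 7.4.

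The cost is a short text amendment, the investigators' time to choose the EEG measures, and the IRB approval that Section 14.7 requires before an amendment is implemented. No new data, visits or patients are needed.
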